12.4.5 Sensitivity analyses for primary endpoint/estimand

After receiving antimalarial medication, a participant's parasite usually decreases log-linearly after a lag stage ([White 2011](#), [Flegg et al 2011](#)). For artemisinin derivatives, parasitemia starts to decline in a log-linear manner almost as soon as parasiticidal drug concentrations are reached ([White 2011](#)). The T_{max} is about 0.5 to 15 minutes for IV artesunate ([Artesunate PI](#)). The T_{max} is about 4 hours for oral cipargamin and should be much shorter for IV cipargamin. Missing data of parasite counts at 12 hours could be well estimated using a log linear interpolation of the 2 parasite counts immediate before and after 12 hours. Since there are 3 planned parasite assessments on or after 2 hours, missing parasite count at 12 hours due to early discontinuation could be estimated using participant specific log linear regression if there are at least 2 parasite counts prior to the discontinuation. A sensitivity analysis will be performed using interpolation for missing data at intermediate time points and extrapolation using a log linear regression if there are at least 2 parasite counts prior to discontinuation. In the event that a participant does not have at least 2 parasite counts prior to discontinuation, the participant will be imputed as not achieving $\geq 90\%$ reduction at 12 hours. Parasite counts below the limit of detection will be substituted using the half limit of detection.

The severity of disease is different between Cohort 1 and Cohort 2, which might impact the ability to achieve $\geq 90\%$ parasite reduction, ie., resulting in a different binomial distribution between Cohorts 1 and 2. Therefore, two-sided 90% confidence intervals (CI) for the difference between each IV cipargamin dose regimen vs IV artesunate will be provided for Cohort 1 and Cohort 2 separately, using handling of missing values not related to intercurrent events specified in [Section 12.4.4](#) and in this section.

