Analysis of secondary endpoints related to parasite clearance dynamics

All analyses will be performed using the FAS.

Proportions of participants with ≥ 90% *P. falciparum* asexual parasite reduction from baseline at 24 and 48 hours: missing data due to intercurrent and non-intercurrent events will be handled similar to the primary efficacy endpoint (See [Section 12.4.3](#), [Section 12.4.4](#)). These 2 variables will be analyzed using the statistical methods specified in [Section 12.4.2](#), [Section 12.4.5](#) and [Section 12.4.6](#).

PRRs at 12, 24 and 48 hours: PRR is defined as the ratio of asexual parasite at baseline divided by asexual parasite at post-baseline. If the asexual parasite count at post-baseline is 0, the half value of detection limit will be used to calculate the ratio. Missing values will not be imputed. For each PRR, 2-sided 90% CIs for each treatment group and for treatment ratio between each IV cipargamin regime vs IV artesunate by cohort will be provided using an analysis of covariance (ANCOVA) model on the log scale with log baseline value as a covariate and treatment group as a factor. For all cohorts pooled, the analysis will be performed with cohort as an additional factor in the ANCOVA model.

PCT and FCT: PCT will be calculated based on uncorrected *P. falciparum* asexual parasite counts. If a participant does not experience an event (such as *P. falciparum* parasite clearance, etc.), the time to the event will be censored at the last relevant assessment (such as last *P. falciparum* parasite assessment, etc.) participants who do not have the health condition at baseline (eg, fever, etc.) will be excluded from the corresponding time to event analysis (eg., FCT, etc.). Descriptive statistics will provided using the Kaplan-Meier method and Kaplan-Meier curves will be presented by treatment and cohort. For all cohorts pooled, difference for the cipargamin regimen vs artesunate will be evaluated using a log-rank test stratified by cohort. Two-sided 90% CIs for the hazard ratio will be provided.

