PCE slope half-life: PCE slope half-life will be calculated for each participant using the WWARN (World Wide Antimalarial Resistance Network) Parasite Clearance Estimator as described in [Flegg et al 2011](#). 2-sided 90% CIs for each treatment group and for treatment ratio between each IV cipargamin regime vs IV artesunate by cohort will be provided using an analysis of covariance (ANCOVA) model on the log scale with log baseline value as a covariate and treatment group as a factor. For all cohorts pooled, the analysis will be performed with cohort as an additional factor in the ANCOVA model.

Incidence of recrudescence and reinfection during the study

Reinfection is defined as appearance of asexual parasites after clearance of initial infection with a genotype different from those parasites present at baseline.

Recrudescence is defined as appearance of asexual parasites after clearance of initial infection with a genotype identical to that of parasites present at baseline. Recrudescence must be confirmed by PCR analysis.

Incidence rates of recrudescence and reinfection at Study Day 29 will be estimated by Kaplan-Meier method based on the subset of FAS participants who have clearance of initial infection by Study Day 7. Time to recrudescence/reinfection will be calculated from the time of first IV study medication to the date of first event if a participant experience the event and be censored at the time of last parasite assessment if a participant does not experience the event.

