Fever Clearance time (FCT) (in patients with temperature of $\geq 37.5^{\circ}\text{C}$ axillary or $\geq 38.0^{\circ}\text{C}$ oral/tympanic/rectal) is defined as time from the first IV study medication until the first time the body temperature decreased below and remained below 37.5°C axillary or 38.0°C oral/tympanic/rectal for at least a further 24 hours,

Parasite clearance time (PCT) is defined as time from the first IV study medication until the first total and continued disappearance of asexual parasite forms which remained at least a further 48 hours.

Parasitaemia: P. falciparum asexual parasite counts are based on the local lab assessment for all cohorts and repeated using central lab assessments for Cohorts 1 and 2. Similar use of local lab readings and central lab readings will be applied to PRR, recrudescence, reinfection, and clinical success below.

Parasite detection limit for central lab: 0.1 parasite/uL will be used as detection limit or assay sensitivity limit for the parasite counts using the central lab.

Parasite detection limit for local lab: 10 parasite/uL will be used as detection limit or assay sensitivity limit for the parasite counts using the central lab.

PRR is defined as the ratio of asexual parasite at baseline divided by asexual parasite at post-baseline. If the asexual parasite count at post-baseline is 0, the detection limit will be used to calculate the ratio.

Recrudescence and reinfection

Recrudescence is defined as appearance of asexual parasites after clearance of initial infection with a genotype identical to that of parasites present at baseline. Recrudescence must be confirmed by PCR analysis.

Reinfection or new infection is defined as appearance of asexual parasites after clearance of initial infection with a genotype different from those parasites present at baseline.

Clinical success

Clinical success is a composite endpoint defined based on the following criteria.

A patient is said to have achieved the clinical success at a given timepoint if the patient did not die either during the initial hospitalization nor due to malaria post the initial hospitalization, shows absence of *P. falciparum* asexual parasites, and did not have any of the key signs or symptoms of severe malaria on that given timepoint.

Note: Deaths occurring post initial hospitalization will be evaluated by designated adjudication committee to confirm if they are related to malaria.

Key signs of Severe Malaria

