2.7.2.4 Time to event analyses

Time to event will be calculated from the time of first study medication to the date of first event if a patient experiences the event and be censored at the time of last assessment if a patient does not experience the event. Randomization date will be used in the absence of study medication date.

For the following time to event variables, the first visit with the event will be used to calculate the time if a patient experiences the event. If a patient does not experience the event, the time will be censored at the last visit assessment for the specific type of event (such as last sit assessment, etc.) with the exception of date of discontinuation (or death) for time to oral antimalarial therapy.

- Time to *P. falciparum* asexual parasite clearance (PCT) (in hours)
- Time to fever clearance (FCT) (in hours)
- Time to oral antimalarial therapy (in hours),
- Time to recover prostration (in hours) in patients who are prostrated at baseline

Descriptive statistics (mean, standard error, median, quartiles) will be presented using the Kaplan-Meier method by treatment and cohort. Kaplan-Meier curves will be provided by treatment and cohort. For all cohorts pooled, difference for the cipargamin regimen vs artesunate will be evaluated using a log-rank test stratified by cohort (Cohorts 1 and 2 pooled as one cohort). Two-sided 90% CIs for the hazard ratio will be provided.

PCT will be calculated based on *P. falciparum* asexual parasite counts. Patients without parasite clearance for whatever reason will be censored at the time of last parasite assessment. Patients who received any non-study IV antimalarial medication (including IV rescue medication) before parasite clearance will be censored at the first use of antimalarial medication.

Patients who did not have a fever at pre-dose will not be included in the analysis of FCT. Patients without fever clearance for whatever reason will be censored at the time of last temperature assessment. Patients who received any antimalarial medication (including rescue medication) before fever clearance will be censored at the first use of antimalarial medication.

Patients without switching to oral medication for whatever reason will be censored at the time of last study assessment. Patients who received any IV rescue medication will be censored at the first use of IV rescue medication.

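### The pooled comparison of parasite clearance time leaves out baseline parasite count, at a modest cost in power

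*Protocol*

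**What the plan says.** - **PCT.** Protocol 12.5.1 specifies, for the between-arm comparison: "For all cohorts pooled, difference for the cipargamin regimen vs artesunate will be evaluated using a log-rank test stratified by cohort". SAP 2.7.2.4 gives the same test with Cohorts 1 and 2 as one stratum, and adds "Two-sided 90% CIs for the hazard ratio will be provided". SAP Table 2-11 lists a stratified log-rank test and a hazard ratio, for pooled cohorts only. Baseline parasite count appears in none of these places. The model that yields the hazard ratio is not named; SAP 5.8.3 gives only PROC LIFETEST for Kaplan-Meier and log-rank.
- **PRR and PCE slope half-life.** Protocol 12.5.1 and SAP 2.7.2.5 analyse both by an "analysis of covariance (ANCOVA) model on the log scale with log baseline value as a covariate and treatment group as a factor", with cohort added when cohorts are pooled.
- **Mechanism.** Protocol 12.4.5 says that a "participant's parasite usually decreases log-linearly after a lag stage".
- **Detection limit.** SAP 2.1.1: "Parasite detection limit for local lab: 10 parasite/uL will be used as detection limit".
- **Status.** SAP 2.7.2 states that the secondary endpoints carry no pre-specified hypotheses.

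**The concern.** If counts fall in a straight line on the log scale, then apart from any lag the time to reach the detection limit is the log distance to travel divided by the clearance rate. The starting count sets that distance. PRR already divides by baseline, and half-life is a slope, so both remove much of this dependence by construction. PCT removes none of it, yet it is the one of the three left unadjusted.

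Cohort is a weak stand-in. Cohorts 2 to 5 share a floor of 5,000/µL with no upper limit in the inclusion criterion. Cohort 1 (60,000 to 250,000/µL) is merged with Cohort 2 into one stratum.

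The plan gives no reason for the omission. SAP 2.1 drops the randomisation factors because strata would be small, but one continuous covariate creates no strata. At stake are some power in the pooled test, a hazard ratio attenuated towards 1, and consistency across three related endpoints.

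**Working it through.** **1. The plan's own size.** No power, event count or hazard ratio is stated for PCT. The only size for the pooled comparison is 107 evaluable per arm, set for clinical success at 48 hours (Protocol 12.8.2). It reproduces: with p = 0.75 in both arms, the probability that the Newcombe 90% CI half-width is at most 0.1 is 0.838 at n = 107 and 0.790 at n = 106. Inflating for 8% exclusion gives 107/0.92 = 116.3, against 116 stated. If all 214 participants clear, Schoenfeld's formula at two-sided 10% gives power 0.61 for a hazard ratio of 1.3 and 0.79 for 1.4.

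**2. Dependence of PCT on baseline.** PCT ≈ lag + ln(baseline/limit)/rate. With a limit of 10/µL, no lag and equal rates:
- entry at 250,000/µL: ln(25,000) = 10.13
- entry at 5,000/µL: ln(500) = 6.21
- ratio 10.13/6.21 = 1.63

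This compares two individuals, not two arms.

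**3. Chance imbalance between arms.** Assume an SD of ln baseline of 0.8 to 1.2 and a centre of 50,000/µL (neither is in the documents).
- SE of the difference in mean ln baseline = SD × √(2/107) = 0.11 to 0.16
- relative to ln(50,000/10) = 8.5, a one-SE imbalance shifts PCT by 1.3% to 1.9%
- on a 44-hour median that is about 0.6 to 0.85 h

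**4. Efficiency, by simulation.** 107 per arm in four strata, PCT read on the protocol's blood-film schedule. Assumed, not documented: SD of ln baseline 0.8 to 1.2 (capped at 500,000/µL, Cohort 1 limits kept), SD of ln half-life 0.2 to 0.5, artesunate median half-life 3.3 h (median PCT about 44 h), no lag, no censoring. Small effects: half-life ratio 0.86 to 0.94.

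| Quantity | Without log baseline | With log baseline |
|---|---|---|
| Variance of log-rank statistic (relative) | 1 | 0.78 to 0.98 |
| Log-rank power, small effect | 59% to 65% | 63% to 67% (+1.6 to +7.0 points) |
| Log-rank rejection under the null | 9.5% to 10.9% | 9.6% to 11.1% |
| Cox power, small effect | 51% to 60% | 55% to 63% (+1.5 to +9.8 points) |
| SE of log hazard ratio | 0.139 to 0.140 | 0.140 to 0.141 |
| Hazard ratio, example scenario | 1.24 | 1.30 |

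The variance ratios convert to 1/0.98 = 1.02 and 1/0.78 = 1.28 (1.29 from the unrounded 0.777), so about 2% to 29% more participants. A linear model on log PCT, which needs no proportional hazards, gives similar ratios (0.77 to 0.97).

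The Cox rows need a caution. PCT on a fixed smear schedule is heavily tied. With Efron's method the Wald test was often conservative under the null: 5.5% to 10.7% rejection without the covariate and 7.5% to 10.0% with it (400 runs each). Part of the Cox gain may reflect that, and the adjusted Cox test did not beat the plain log-rank test in every scenario.

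**5. At the effect the documents point to.** Protocol 1.1 cites a median PCT under 12 h for oral cipargamin. SAP 5.8.4 expects over 40 h for artesunate. With simulated medians of 13.7 h and 43.9 h, the unadjusted log-rank test rejected in 200 of 200 runs (smallest |z| 11).

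**The case against.** The strongest case for the plan has four parts.

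1. The stratified log-rank test is valid under randomisation, and a typical chance imbalance moves PCT by under an hour. This stands. A reader might infer that the PCT comparison is biased or invalid; the documents do not support that.
2. Adjustment does not sharpen the requested interval. This also stands. A reader might infer that precision is being thrown away and that the 90% CI would narrow, but the SE of the log hazard ratio does not fall. The hazard ratio moves away from 1 because hazard ratios are non-collapsible, so the adjusted one is a different, conditional quantity.
3. Baseline-adjusted comparisons of clearance already exist in PRR and half-life. That is true, but PCT is a listed secondary endpoint with its own reported hazard ratio, so they do not replace it.
4. The log-linear mechanism stretches time and does not imply proportional hazards linear in log baseline. That is fair. The covariate is a working adjustment, although the planned hazard ratio already leans on proportional hazards for treatment.

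Two further inferences should be resisted. It is tempting to say that the loss is worst in the small cohorts, but PCT is compared between arms only with cohorts pooled (Table 2-11). It is also tempting to extend the point to fever clearance time in the same paragraph, but the argument from starting count and detection limit does not apply there.

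**Conclusion.** The point holds as a minor matter of efficiency and consistency. The pooled PCT analysis omits a recorded baseline variable that directly drives the endpoint and that the same section uses for two related endpoints. For small effects the loss is worth about 2% to 29% of participants. That range rests on spreads of baseline count and clearance rate that the documents do not give, and on no lag and no censoring. If the effect is near what the documents suggest, the test is decisive with or without the covariate; the cipargamin figure there comes from oral dosing in uncomplicated malaria. Exploratory analyses are blacked out, so an adjusted PCT analysis there cannot be ruled out.

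**What to change.** In Protocol 12.5.1 and SAP 2.7.2.4, keep the cohort-stratified log-rank test as specified. Name the model behind the PCT hazard ratio and its 90% CI: Cox, stratified by cohort (Cohorts 1 and 2 combined), with log baseline *P. falciparum* count as covariate. State that the hazard ratio is conditional on baseline count, and say how ties are handled. Carry this into SAP Table 2-11 and SAP 5.8.3.

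The cost is a short model specification, which the unnamed hazard ratio needs anyway, and no new data. The small downside is that the hazard ratio becomes conditional and no longer corresponds exactly to the unadjusted log-rank test beside it.

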12.5.2 Safety endpoints

For all safety analyses, the safety set will be used. All listings will be presented by cohort, treatment group, participant and visit/time if applicable. Summary tables will be presented by cohort (including pooled cohort,) and treatment group.

Secondary safety endpoints include:

- Standard safety/tolerability assessments (incidence of serious adverse events (SAEs), mortality, in-hospital mortality, adverse events (AEs), and routine safety and laboratory assessments)
- Proportion of participants developing early hemolysis after treatment (as defined in [Section 10.2.3](#)).
- Proportion of participants developing delayed hemolysis after treatment (as defined in [Section 10.2.3](#)).

Adverse events

All information obtained on adverse events will be displayed by cohort, treatment group and participant.

The number (and percentage) of participants with treatment emergent adverse events (events started after the first dose of study medication or events present prior to start of double-blind treatment but increased in severity based on preferred term) will be summarized in the following ways:

- by cohort, treatment, primary system organ class and preferred term.
- by cohort, treatment, primary system organ class, preferred term and maximum severity.
- by cohort, treatment, Standardized MedDRA Query (SMQ) and preferred term.

Separate summaries will be provided for study medication related adverse events, mortality, in hospital mortality, mortality related to malaria by adjudication, serious adverse events, other significant adverse events leading to discontinuation, and adverse events leading to dose adjustment. Summaries will also be provided separately for adverse events occurring during the IV study period (prior to oral standard of care, Coartem) and for adverse events post the IV study period (after taking oral Coartem).

The number (and proportion) of participants with adverse events of special interest/related to identified and potential risks will be summarized by cohort and treatment.

A participant with multiple adverse events within a primary system organ class is only counted once towards the total of the primary system organ class.

Vital signs

All vital signs, body height, body weight, and head circumference data will be listed by cohort, treatment group, participant, and visit/time. If ranges are available, abnormalities (and relevant orthostatic changes) in vital signs will be flagged and listed by cohort, treatment group, participant, and visit/time. Summary statistics will be provided by cohort, treatment group, and visit/time.

12-lead ECG

Abnormal ECG data will be flagged and will be listed by cohort, treatment group, participant and visit/time. Summary statistics may be provided by cohort, treatment group and visit/time.

The analysis results for categorical outliers and T-wave morphology will be summarized in frequency tables with counts and percentages for both number of participants and number of

timepoints. For categorical outliers, the number of participants (%) and timepoints will be determined by treatment group for the following:

- increase in QTcF from baseline of ≥ 30 msec and ≥ 60 msec
- increase in QTcB from baseline of ≥ 30 msec and ≥ 60 msec
- absolute QTcF values > 450 msec, > 480 msec, and > 500 msec
- absolute QTcB values > 450 msec, > 480 msec, and > 500 msec
- PR change from baseline $> 25\%$ increase resulting in PR > 200 msec
- QRS change from baseline $> 25\%$ increase resulting in QRS > 120 msec
- heart rate change from baseline $> 25\%$ decrease resulting in heart rate < 50 beats per minute
- heart rate change from baseline $> 25\%$ increase resulting in a heart rate > 100 beats per minute

For T-wave morphology, the analysis will be focused on the treatment emergent changes.

The relationship between change from baseline in QTcF/QTcB and cipargamin plasma concentration will be assessed graphically with change from baseline in QTcF/QTcB plotted against cipargamin plasma concentrations.

This concentration-QT relationship may also be explored using linear mixed effects model ([Garnett et al 2018](#)). The change from baseline in QTcF/QTcB will be the dependent variable in the model, baseline QTcF/QTcB, cipargamin treatment flag (yes or no) cipargamin plasma concentrations as a covariate and time as a categorical variable. A random intercept for each participant will be specified. Control (artesunate) participants will be included in the analysis with a plasma concentration of 0. The control-corrected change from baseline in QTcF/QTcB and the two-sided 90% confidence interval will be extracted from the model at the geometric mean maximum plasma concentration for cipargamin.

Clinical laboratory evaluations

If normal ranges are available, abnormalities in laboratory data will be flagged and will be listed by cohort, treatment group, participant, and visit/time and. Summary statistics will be provided by cohort, treatment, and visit/time. Shift tables using the low/normal/high/ (low and high) classification will be used to compare baseline to the worst on-treatment value.

The number (and proportion) of participants with early hemolysis and number (and proportion) of participants with delayed hemolysis (see [Section 10.2.3](#)) will be summarized by visit, cohort, and treatment group.

The number (and proportion) of participants with serum lactate < 2 mmol/l will be summarized by visit (8, 12, 36, 48, and 72 hours), cohort and treatment group in participants with hyperlactemia (serum lactate > 4 mmol/L) at baseline.

The percentage change from baseline in plasma lactate level will be summarized by visit (4, 8, 12, and 24 hours), cohort and treatment group.

The time to normalized blood lactate level (in hours) in participants with baseline blood lactate level above normal will be summarized descriptively using the Kaplan-Meier method by cohort

and treatment group. Kaplan-Meier curve will be also presented. If a participant does not normalize the blood lactate, the time will be censored at the last blood lactate assessment.

